5.9 Exploratory Analyses

Objective:	Data Variables:	Data Source:
Identify COVID-related mortality at Day 28 in study participants and matched controls	
 Flag of infusion treatment Demographics Elixhauser conditions Symptoms 	
 Optum infusion pharmacy data UHC claims data CDSM COVID labs data BCRT COVID hospitalizations data Optum EMR data

Commented [WWY49]: May not need this table.

The exploratory objective is to determine the incidence of COVID-related mortality at Day 28 among Bamlanivimab-treated patients relative to external controls. We will perform descriptive analysis and report summary statistics if there will be COVID deaths in study participants and matched controls.

5.10 Safety Analyses

The two safety objectives are:

1. To describe the incidence of infusion reactions during receipt of infusion and during the defined infusion follow-up period (follow-up period to be consistent with EUA fact sheet for healthcare providers)
2. To describe the incidence of patient reported adverse event (AE) outcomes through Day 28

Commented [WWY50]: This section should add such as Reporting by System Organ Class (SOC) and PT. Please refer to the sample SAP

Commented [JA51R50]: We're checking internally and will keep you posted.

Objective:	Data Variables:	Data Source:
Identify any infusion reactions during receipt of infusion and during the infusion follow-up period	
 Infusion reactions Date of infusion treatment Date of infusion reactions of interest Demographics Elixhauser conditions 	
 Optum infusion pharmacy data UHC claims data

Clinicians will start with qualitative analysis a case by case. We will report descriptive statistics according to the data we will obtain. If we have a sufficient size of study participants with particular infusion reactions, we can calculate descriptive statistics, run Chi-square independence test and Kruskal-Wallis test to examine if infusion reactions vary from demographics or comorbidities.

Objective:	Data Variables:	Data Source:
Identify any self-reported adverse events between receipt of infusion and day 28 from study participants	
 • Adverse events • Date of infusion treatment • Date of infusion reactions of interest • Demographics • Elixhauser conditions 	
 • Optum infusion pharmacy data • UHC claims data

We will perform the same methodology described above given the AEs and serious AEs defined in Section 5.10.1.2.

5.10.1.1 **Extent of Exposure**

Exposure to therapy will be represented as the total number of complete and incomplete infusions, and will be summarized using descriptive statistics.

Commented [ATJ52]: To Lilly: I'm not sure what requires in this section and if we need it.

Commented [XM53]: Exposure to therapy will be represented as the total number of complete and incomplete infusions, and will be summarized using descriptive statistics.

Commented [JAT54R53]: Thanks. Added the texts.

5.10.1.2 **Adverse Events**

The current list of AEs comes from the Phase 2 trial of ambulatory participants and a reasonable anticipation of serious AEs for this study.

The most commonly reported AEs from the Phase 2 trial include:

- Nausea
- Diarrhea
- Dizziness
- Headache
- Pruritus
- Vomiting

The reasonably anticipated serious AEs include:

- Secondary infection – pneumonia, sepsis
- Respiratory failure requiring non-invasive or invasive mechanical ventilation – acute respiratory distress syndrome (ARDS)
- Major acute cerebrocardiovascular event – cardiovascular death, myocardial infarction, hospitalization for unstable angina, hospitalization for heart failure, serious arrhythmia, resuscitated sudden death, cardiogenic shock due to myocardial infarction, coronary revascularization procedure, neurologic stroke, and peripheral vascular events
- Coagulopathy
- Acute kidney injury – renal replacement therapy
- Multi-organ dysfunction syndrome

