Table A10. Summary of the sensitivity analyses.

Statistic/Method	Results
E-value (95% CI)	
ε (95% CI)	

Commented [XM62]: Add tables for the death results and safety analyses

Commented [JAT63R62]: I add Table A12 and A12.2 for safety analyses. No tables for all-cause death since it's not the primary outcome here.

Dataset: dataset location (data table name with the corresponding database in Google BigQuery)

Program: program location/program name.R

Output: output location/output name.csv or .xlsx

Table A11. Standardized difference in mean and variance ratio of all matching covariates before double score matching

Variable	Standardized difference in mean	Variance ratio

LY3819253

CONFIDENTIAL

[Protocol number: UHG (J2X-NS-I002)] SAP [v.3]

Age (continuous or categorical): 65- 65 – 69 70 – 74 75 – 79 80+* *: We can separate 80+ into finer groups as needed.	
Gender	
Race: White Black Asian Hispanic Other	
Urbanization of residence: Urban Suburban Rural	
Socioeconomic index	
Dual status With Medicaid Elixhauser comorbidity score	
Elixhauser conditions* *: There are 29 conditions in total as shown in Table A1.	
Immunosuppressive treatment 6 months prior to date of COVID diagnosis	

LY3819253

CONFIDENTIAL

[Protocol number: UHG (J2X-NS-I002)] SAP [v.3]

Dataset: dataset location (data table name with the corresponding database in Google BigQuery)

Program: program location/program name.R

Output: output location/output name.csv or .xlsx

Repeat Table A11:

Table A11.2

Standardized difference in means and variance ratio of all matching covariates after double score matching

Double score matched population

Programming notes:

Replace “before double score matching” with “after double score matching” in the table title.

Table A12. Listing of adverse events (AEs) for study participants.

Commented [JAT64]: We're checking this information internally and will keep you posted.

Patient ID	Age/Gender	AE*	Start/Stop date	No. of days after the Bamlanivimab infusion

*: adverse events (AEs) include nausea, diarrhea, dizziness, headache, pruritus, and vomiting.

We will report the table if available.

Repeat Table A12:

Table A12.2

Listing of serious adverse events (SAEs) for study participants.

Programming notes:

Replace “SAE” with “AE” in the column of AE.

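### SAP 5.10 takes its AE and SAE definitions from two lists of expected events; if these are applied as definitions, unlisted events drop out of the Day 28 incidence

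*SAP*

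**What the plan says.** SAP 5.10 sets a broad aim for the second safety objective: "Identify any self-reported adverse events between receipt of infusion and day 28 from study participants". The method that follows is narrower: "We will perform the same methodology described above given the AEs and serious AEs defined in Section 5.10.1.2".

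Section 5.10.1.2 opens by giving the source of its content: "The current list of AEs comes from the Phase 2 trial of ambulatory participants and a reasonable anticipation of serious AEs for this study". Two bulleted lists follow, one of common Phase 2 AEs and one of anticipated SAEs. Within the SAE list, one item covers "cardiovascular death, myocardial infarction, hospitalization for unstable angina, hospitalization for heart failure" and other cardiac, neurologic and vascular events.

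In SAP Appendix 3, the note to Table A12 reads "adverse events (AEs) include nausea, diarrhea, dizziness, headache, pruritus, and vomiting". The note to Table A12.2 does the same for the SAE categories. A margin reply there says "I add Table A12 and A12.2 for safety analyses. No tables for all-cause death", giving as the reason that death is not the primary outcome.

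Two matters are still open in the margins. Comment 50 on section 5.10 says "This section should add such as Reporting by System Organ Class (SOC) and PT", and the reply is that this is being looked into. The comment on Table A12 says the team is "checking this information internally and will keep you posted".

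**The concern.** A list of events that one expects to see is not a definition of what counts as an adverse event. The SAP uses such a list where the definition should stand, and the table notes a programmer would work from carry the same list.

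The objective is the incidence of patient-reported AEs through Day 28. Protocol section 2 places it among the primary objectives; protocol 6.5 and SAP 3.3 call it secondary. If the lists act as a filter, the result is the incidence of pre-selected events, presented as the incidence of all AEs. Such a filter would miss the unexpected events, which matter most when an infusion is moved into the home. Two programmers could follow this SAP faithfully and report different figures.

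**Working it through.** The plan gives no AE rate, so there is no figure to reproduce. The check sets the texts side by side.

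**1. Where the definition should come from.** Protocol 6.5.5 makes the AE analysis wait until AEs have been defined or classified and adjudicated. SAP 5.10 points to 5.10.1.2 for the definition. SAP 5.14 records no change from the protocol's planned analyses.

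**2. What 5.10.1.2 contains.**
- AE terms: nausea, diarrhea, dizziness, headache, pruritus, vomiting = 6.
- SAE categories: secondary infection, respiratory failure requiring ventilation, major acute cerebrocardiovascular event, coagulopathy, acute kidney injury, multi-organ dysfunction = 6.
- It has no general AE definition, no seriousness criterion, no coding rule and no rule for an unlisted event.

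**3. What the mock tables contain.** The A12 note has the same 6 terms and the A12.2 note the same 6 categories. Both are by-patient listings. Neither gives a count over a denominator.

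**4. Comparison with the protocol on seriousness.** Protocol 9.1 treats seriousness by outcome, and death and hospitalization appear there without a named cause. In SAP 5.10.1.2, death is named for 1 cause (cardiovascular) and hospitalization for 2 (unstable angina, heart failure), all inside one category. A non-COVID hospitalization, or a non-COVID and non-cardiovascular death, can therefore be serious under 9.1 and lie outside all six categories.

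**5. Comparison with what is asked of participants.** The symptom checker in SAP Appendix 2 marks new loss of sensation and new loss of strength in an extremity as high priority. Neither is among the 6 AE terms. The checker also asks an open question about any other symptom, so capture is wider than the lists.

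**6. Effect on the reported incidence.** Let N be the infused participants, L those with at least one listed AE, and U those whose only AEs are unlisted.
- Lists as definition: L / N.
- All reported AEs: (L + U) / N.
- Difference: (L + U) / N − L / N = U / N, which is zero or positive.

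A participant with both listed and unlisted AEs is counted either way. The same algebra holds for SAEs. The documents give no value for U, so the direction is known and the size is not.

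**The case against.** The strongest reply is that the lists were never meant to be closed. Section 5.10.1.2 calls its content current and speaks of events that are common or reasonably anticipated. Both lists and both table notes use *include* or *includes*, the aim covers any self-reported event, and the data variable is simply adverse events. Clinicians first review case by case, and statistics follow the data obtained. No sentence excludes an unlisted event. All of this stands. A reader might infer that the SAP restricts the analysis to twelve items, and the documents do not support that. They leave two readings open and do not say which governs.

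A reader might also infer that an unlisted death or hospitalization has no place in any mock table. That holds only on the closed reading: A12 and A12.2 have no preset event rows, so an unlisted event could be entered. The margin reply on all-cause death answers a request for death tables and does not say that deaths are kept out of A12.2.

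Protocol 9.1 words seriousness in two ways, one for the IRB and a longer one for the manufacturer. It would be too strong to call these rival analysis definitions, because both are written as reporting duties.

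Other points limit the consequence. The objective names patient-reported AEs and not SAE incidence as such. The safety analysis is single-arm and descriptive, with no decision rule tied to the lists. The interim safety report to the FDA runs under protocol 9.1. SOC/PT reporting has already been requested. The embedded CRFs, which cannot be seen here, may hold AE definitions.

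None of this supplies the missing rule. SAP 5.10 still names 5.10.1.2 as the definition and analyses SAEs on that basis.

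**Conclusion.** The point holds as an ambiguity in the SAP with a consequence in one direction. If the lists are applied as the definition, unlisted AEs are left out, as are events serious by outcome under protocol 9.1 but outside the six categories. Reported participant-level incidence can then only be equal to or lower than the true reported figure, by U/N. The documents do not allow U/N to be computed. If the lists are read as examples, nothing is lost.

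This concerns the analysis and its displays only. Data capture, IRB and manufacturer reporting, and the separate analyses of infusion reactions, COVID hospitalization and COVID death stand as planned. The SAP should be corrected before the safety tables are programmed. Confidence is medium, because the open reading is plausible and the CRFs are not visible.

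**What to change.** Reword SAP 5.10.1.2 to state that:
- all AEs reported from infusion to Day 28 are analysed, whether or not they are listed;
- SAEs are classified by outcome, consistent with protocol 9.1, with the outcomes written out, and relatedness and expectedness do not filter the analysis;
- the two lists are expected events only.

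Change the notes to Tables A12 and A12.2 to match. Because the objective is incidence and these tables are listings, add a summary of n/N participants with at least one AE and with at least one SAE. N is the infused participants whom SAP Table 3 already assigns to the safety analysis. SOC/PT coding can follow the request already open in comment 50.

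The cost is a few sentences of SAP text, two table notes, one summary shell and a small amount of extra coding. Data collection and clinical procedures do not change.

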5.11 Protocol Violations

Protocol deviations will be identified throughout the study. Important protocol deviations (IPDs) are defined as those deviations from the protocol that would potentially compromise participants' safety, data integrity, or study outcome.

The number and percentage of participants having IPDs will be summarized within category and subcategory of deviations. A by-patient listing of IPDs will be provided.

5.12 Other Analyses

Objective:	Data Variables:	Data Source:
Evaluate the association of the time gap between a COVID positive test result and an infusion with COVID hospitalization	
• Date of symptoms onset• Date of COVID diagnosis• Date of infusion treatment• Date of COVID hospitalization• Demographics• Elixhauser conditions	
• Optum infusion pharmacy data• UHC claims data• CDSM COVID labs data• ProtectWell data
Evaluate the association of the time gap between a symptom onset and an infusion with COVID hospitalization		

There are two pre-specified analyses we will pursue aside from the primary, exploratory and safety objectives in the previous sections.

First, we want to understand if the timing of the infusion relative to a positive COVID test, impacts hospitalizations. We will compute the Cramer's V and phi coefficient as one-number summary of correlation between two categorical variables when we group time gap between date of COVID positive and date of home infusion. If considering this time gap as a continuous variable, we will run a simple logistic regression model to examine if time gap is associated with the hospitalization rate at Day 28. Then, we will apply the same methodology described above for categorical and continuous covariates and binary outcomes.

Second, we want to understand if the timing of the infusion relative to a symptom onset, impacts hospitalizations. We will compute the Cramer's V and phi coefficient as one-number summary of correlation between two categorical variables when we group time gap between date of COVID positive and date of home infusion. If considering this time gap as a continuous variable, we will run a simple logistic regression model to examine if time gap is associated with the hospitalization rate at Day 28. Then, we will apply the same methodology described above for categorical and continuous covariates and binary outcomes.

CONFIDENTIAL

[Protocol number: UHG (J2X-NS-I002)] SAP [\[v.3\]](#)

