6.5.6 Subgroup Analysis

Research Questions:	Data Variables:	Data Source:

Is the time gap between a COVID positive test result and an infusion associated with COVID hospitalization?
 
Do we find any patterns in a subgroup with certain demographic characteristics or comorbidities of interest?
	
 • Flag of infusion treatment • Demographics • Elixhauser conditions • Symptoms 	
 • Patient self-reported data • Optum infusion nurse data • UHC claims data • CDSM COVID labs data • ProtectWell data

There are two pre-specified subgroup analyses we will pursue aside from the primary and secondary objectives (efficacy and safety) above.

First, we want to understand if the timing of the infusion relative to a positive COVID test, impacts hospitalizations. We will compute the Cramer's V and phi coefficient as one-number summary of correlation between two categorical variables when we group time gap between date of COVID positive and date of home infusion. If considering this time gap as a continuous variable, we will run a simple logistic regression model to examine if time gap is associated with the hospitalization rate at Day 28. Then, we will apply the same methodology described above for categorical and continuous covariates and binary outcomes.

Second, we want to understand if the timing of the infusion relative to a symptom onset, impacts hospitalizations. We will compute the Cramer's V and phi coefficient as one-number summary of correlation between two categorical variables when we group time gap between date of COVID positive and date of home infusion. If considering this time gap as a continuous variable, we will run a simple logistic regression model to examine if time gap is associated with the hospitalization rate at Day 28. Then, we will apply the same methodology described above for categorical and continuous covariates and binary outcomes.

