4.4 Study Population

4.4.1 Selection Criteria

Both study participants and matched controls will meet the inclusion and exclusion criteria below.

Inclusion Criteria:

- Age 65+, confirmed SARS-CoV-2 positive, located in an area where Bamlanivimab (LY3819253) is available for infusion
- Have mild or moderate COVID-19 symptoms (after stage 1 of symptom tracking)

Commented [JAT4]: Update to keep the same criteria in the latest protocol (version 10 on Feb 3, 2021).

Commented [JAT5]: Remove it as it is no necessary for active participants and controls.

- Control only: Confirmed symptomatic COVID-19 through Optum EMR data.

Exclusion Criteria:

- Current (from first symptom report) hospitalization for COVID-19
- Prior administration of Bamlanivimab

Commented [JAT6]: Remove as not necessary per the EUA.

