4.5 Endpoints

The following definitions of endpoints hold for all analyses described in this statistical analysis plan. For study participants, we define the study endpoint as 28 days after date of the Bamlanivimab infusion. This holds for both outcomes of COVID-related hospitalization with or without time consideration (i.e., no censoring vs censoring at Day 28). For example, if a study participant hasn't been hospitalized due to COVID-19 within 28 days after COVID-19 diagnosis, we'll treat the binary response of COVID-19 hospitalization as 0 without time consideration. However, with time consideration, it becomes right-censored since this participant may be hospitalized 29 or more days after COVID-19 diagnosis and our observation period is 28 days after COVID-19 diagnosis. More details are described in Section 5.8.1.3. For the pool of potential controls, we define the study endpoint as 28 days after a synthetic date of treatment. We will randomly select a number from the distribution of number of days after date of symptoms onset in study participants to identify an index date with which to define 28 days post infusion where we will monitor claims and EMR data for hospitalizations and mortality.

Commented [WWY14]: Should be the pool of controls which was before PS matching.

Figure 3 illustrates the timeline for study participants and controls to ensure alignment on an index date for symptoms onset and the follow-up period. Since the control group will not have an infusion date associated with them, we will randomly select a number from the distribution of number of days after date of symptoms onset in study participants to identify an index date with which to define 28 days post infusion where we will monitor claims and EMR data for hospitalizations and mortality.

[figure not shown]

Figure 3. Illustration of the timeline for study participants and controls.

For patients who do not experience a COVID-19 related hospitalization by Day 28 following the date of infusion or synthetic treatment, a censoring date is defined as the earliest of 28 days following the date of treatment, or for study participants, the early discontinuation date due to lost to follow-up.

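### The infusion-timing analyses cannot separate the effect of delay from how far the illness has already run; if admission risk falls or peaks early after onset, they are biased toward making late infusion look protective

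*SAP*

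**What the plan says.** SAP 5.12 and Protocol 6.5.6 each set out two pre-specified timing analyses, one for delay from the positive test and one for delay from symptom onset. The text of the first reads "First, we want to understand if the timing of the infusion relative to a positive COVID test, impacts hospitalizations". If the gap is grouped, the tools are Cramer's V and phi. If it is continuous, "we will run a simple logistic regression model to examine if time gap is associated with the hospitalization rate at Day 28". A closing sentence adds "Then, we will apply the same methodology described above for categorical and continuous covariates and binary outcomes". The second analysis is introduced as onset to infusion, but its text still groups by the test-to-infusion gap.

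Three other provisions decide what these analyses measure:

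- **Clock.** SAP 4.5 says "For study participants, we define the study endpoint as 28 days after date of the Bamlanivimab infusion". An example in the same section says "our observation period is 28 days after COVID-19 diagnosis". The two do not agree.
- **Who has a gap.** SAP 4.5 begins its account of the synthetic index date with "Since the control group will not have an infusion date associated with them". Controls get a random draw from the participants' delays. Neither timing section uses that date.
- **Who can be infused.** An exclusion criterion in SAP 4.4.1 is "Current (from first symptom report) hospitalization for COVID-19". Protocol 6.1 allows infusion up to 10 days after onset.

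**The concern.** A participant infused at home on day 9 of illness has, by design, reached day 9 without admission. A participant infused on day 2 still has almost the whole illness ahead. With the 28 days counted from infusion, the two are followed over different stretches of the disease. The gap therefore measures both how late the drug came and how much of the risk period is already over. Among participants alone these cannot be told apart.

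If most admissions occur early, long gaps go with low remaining risk even when timing makes no difference. The analysis could then report fewer hospitalizations with longer delay, or hide a real advantage of early infusion. This applies to both analyses and remains after the wording of the second is corrected.

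**Working it through.** SAP 5.12 gives no sample size, power or effect for these analyses, so there is no stated figure to reproduce. The check asks what the planned regression would show if delay had no effect.

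**Inputs from the documents**
- 1,000 participants and a 15% control rate (SAP 4.4.2 fallback scenario).
- Infusion up to 10 days after onset (Protocol 6.1).
- A 75% reduction with treatment (SAP 4.3), read here as a hazard ratio (HR) of 0.25.

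**Inputs assumed (not in the documents)**
- Onset-to-admission time is lognormal with distribution function F. The central case has median 7 days and sigma 0.5; the range is medians 6-9 and sigma 0.4-0.7.
- Gaps from onset are uniform over 2-10 days.

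**Step 1: remaining risk at gap L, no drug effect.** Risk(L) = p[F(L+28) - F(L)] / [1 - pF(L)], with p = 0.15.
- L = 2: 0.15(0.9982 - 0.0061)/(1 - 0.15 x 0.0061) = 14.9%
- L = 6: 0.15(0.9992 - 0.3789)/(1 - 0.15 x 0.3789) = 9.9%
- L = 10: 0.15(0.9996 - 0.7622)/(1 - 0.15 x 0.7622) = 4.0%

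With a drug effect that does not depend on timing, the risk becomes 1 - [1 - Risk(L)]^HR.

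**Step 2: logistic slope on the gap.** The model was fitted to these expected risks, with 1,000 participants spread evenly over the gaps.

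| Scenario | OR per day | Expected z |
|---|---|---|
| Central case, gaps 2-10, HR 1 | 0.84 | -4.0 |
| Central case, gaps 2-10, HR 0.67 | 0.84 | -3.3 |
| Central case, gaps 2-10, HR 0.25 (about 26 events) | 0.85 | -2.0 |
| Full median and sigma range, gaps 2-10, HR 1 | 0.77-0.90 | -5.2 to -2.5 |
| Full median and sigma range, gaps 2-10, HR 0.25 | 0.78-0.91 | -2.7 to -1.3 |
| Central case, gaps 2-6, HR 1 | 0.89 | -1.7 |
| Central case, gaps 2-6, HR 0.25 | 0.90 | -0.9 |

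**Step 3: other hazard shapes.** A second calculation used infusion on days 1-10, an untreated 38-day risk of 15% or 25%, and no delay effect. The risk ratio for day-10 versus day-2 infusion was:
- constant hazard: 1.00
- falling hazard, half-life 14, 7 or 4 days: 0.68-0.70, 0.46-0.48, 0.25-0.27
- hazard peaking on day 5, 7 or 10: 0.16-0.18, 0.39-0.42, 0.66-0.69
- hazard rising throughout: 1.41-1.46

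At HR 0.25 and 15% baseline, under the falling or early-peak shapes, the chance of a significant result favouring later infusion is 11-67% with 1,000 participants and 52-100% with 7,500. The nominal chance in that direction is 2.5%.

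**Step 4: does a control reference remove it?** Controls were indexed at the same day since onset and still unhospitalized then. With no delay effect and HR 0.25, the ratio of odds ratios per day is 0.996-1.016 for all shapes. If efficacy truly fades from HR 0.25 on day 1 to 0.50 on day 10, that ratio is 1.08-1.09 under the falling or early-peak shapes. The participant-only odds ratio there is 0.88-1.03, which can point the wrong way.

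**The case against.** **Direction.** A reader might infer that late infusion will look protective. The documents do not support that: they give no admission risk by day, and step 3 shows no bias under a constant hazard and the opposite bias under a rising one. A real harm of delay also pulls the other way. With efficacy fading from HR 0.25 on day 1 to 0.67 on day 10, the participant-only odds ratio per day ranges from 0.91 to 1.06. This objection stands, and the direction is stated here as conditional.

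**Size.** The largest z values assume an inactive drug and gaps spread over 2-10 days. Protocol 6.1 calls for infusion as soon as possible, so gaps may be shorter. With gaps of 2-6 days the expected z is only -1.7 or -0.9. This also stands.

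**Association, not effect.** The objective column in SAP 5.12 speaks of association, and the regression tests association. That is fair to the table, but the text beneath it asks about impact, and that is how a reader would take the result.

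**Adjustment and controls.** The reference to earlier methodology may add demographics and comorbidities, and Protocol 6.5.6 lists the treatment flag among its variables. Restriction to participants is thus inferred rather than stated. But those covariates do not carry the time already passed, and no control comparison or interaction is described.

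**The diagnosis clock.** Counting 28 days from diagnosis does not rescue the analysis. It adds time in which a later-infused participant could not have had an event. With onset set 2 days before diagnosis, the day-10 versus day-2 ratio is below 1 under every shape: 0.72-0.74 constant, 0.88-0.89 rising, 0.16-0.67 otherwise.

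**Conclusion.** The concern holds in conditional form. The planned timing analyses mix delay with elapsed illness, and nothing in either document separates them. If admission risk falls with time since onset or peaks within about 10 days, they are biased toward making late infusion look protective and can mask a benefit of early infusion. Under the lognormal assumptions with gaps of 2-10 days, the spurious odds ratio is about 0.77-0.91 per day. Whether it would reach significance with 1,000 participants depends on drug effect and spread of gaps: likely if the drug is inactive and gaps are wide, roughly even in the central case at HR 0.25, and less likely than not with gaps of 2-6 days.

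These analyses sit outside the primary, exploratory and safety objectives. The primary comparison is not affected. The change should be made, but the study does not turn on it.

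**What to change.** In SAP 5.12 and Protocol 6.5.6:

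1. State one follow-up clock, from infusion for participants and from the assigned index date for controls. Reconcile the diagnosis-based example in SAP 4.5 with it.
2. State the gap origin for each analysis: positive test for the first, symptom onset for the second.
3. For these analyses, give each matched control its own participant's gap, measured from that same origin, instead of an unrelated random draw.
4. Require the control to be unhospitalized on that date. If not, replace the control from the pool; drop the pair only if no replacement exists.
5. Test the treatment-by-gap interaction with the gap continuous. Show grouped contrasts descriptively.
6. Keep the participant-only Cramer's V, phi and logistic results as descriptive associations, labelled as not showing an effect of timing.

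The cost is SAP and protocol wording plus one further model on data already planned for collection. The interaction is less precise than the single-group regression, and some controls will need replacing. Control onset dates are also approximate: a comment reply in SAP 4.7 sets onset 2 days before diagnosis. If that rule is applied to participants too, the two gaps differ by a constant and the two regressions have the same slope, so the SAP should say which onset date participants use.
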